3.6. Missing Data and Outliers

3.6.1. Missing Data

A missing data point for a given study visit may be due to any one of the following reasons:

- A visit occurred but data were not collected or were unusable
- A visit did not occur
- A subject permanently discontinued from the study before reaching the window

For analyses of categorical HCV RNA data, if a data point is missing and is preceded and followed in time by values that are “< LLOQ TND”, then the missing data point will be set to “< LLOQ TND”. If a data point is missing and preceded and followed by values that are “< LLOQ detected”, or preceded by “< LLOQ detected” and followed by “< LLOQ TND”, or

preceded by “< LLOQ TND” and followed by “< LLOQ detected”, then the missing value will be set to “< LLOQ detected”; otherwise the data point will be termed a failure (ie, \geq LLOQ detected).

Subjects with missing data due to premature discontinuation of the study will have missing data imputed up to the time of their last dose (for on-treatment displays). If study days associated with the last dosing date is greater than or equal to the lower bound of a visit window, and the value at the visit is missing, then the value will be imputed. If the study days associated with the last dosing date is less than the lower bound of a visit window then the on-treatment value at that visit will remain missing.

If no HCV RNA values are obtained after the last dose of any study drug, the subject will be considered a treatment failure for SVR endpoints. However, success for SVR12 who have no further HCV RNA measurements collected will be counted as a success for SVR24 due to the high correlation between these 2 endpoints {Chen 2013}.

For the analyses of continuous HCV RNA efficacy data for China, any subject with a missing value in a visit window that is bracketed by prior and subsequent values of “< LLOQ TND” will be set to “< LLOQ TND” (ie, 14 IU/mL). Subjects with a missing data point preceded and followed by values that are “< LLOQ detected”, preceded by “< LLOQ detected” and followed by “< LLOQ TND”, or preceded by “< LLOQ TND” and followed by “< LLOQ detected” will be set to “< LLOQ detected” (ie, 14 IU/mL). No other imputation will be performed for continuous data. No Overall analysis of continuous HCV RNA data will be conducted.

For health-related quality of life data (ie, SF-36), missing data will not be imputed.

Except for the imputation rules described above, values for other missing data (including all safety data) will not be imputed.

3.6.2. Outliers

Outliers will be identified during data management and data analysis process, but no sensitivity analyses will be done to evaluate the impact of outliers on efficacy or safety outcomes. All data will be included in the data analysis.

3.7. Visit Windows

3.7.1. Definition of Study Day 1, First/Last Dosing Date, and Baseline

Study Day 1 is defined as the **first dose date of study drug (ie, LDV/SOF)**.

The ***date of last dose of study drug*** will be the end date on study drug administration CRF for the record where the “subject permanently discontinued” flag is ‘Yes’.

Study Day 1 of *post-treatment follow-up* will be ***last dose date of study drug + 1***.

If there are subjects for whom the date of last study drug is unknown due to the reason that the subject was lost to follow-up, the date of last dose will be estimated using the maximum of nonmissing study drug start or stop dates and on-treatment visit dates and laboratory collection dates (post-treatment visits and unscheduled visits are not included).

In general, the *baseline value* will be the last nonmissing value on or prior to the first dose date of study drug. If multiple measurements occur on the same day, the last nonmissing value prior to the time of first dose of study drug will be considered as the baseline value. If these multiple measurements occur at the same time or time is not available, the average of these measurements (for continuous data) or the worst among these measurements (for categorical data) will be considered as baseline value. If multiple ECG measurements occur on the same day prior to first dose of study drug, the average will be used considered as baseline value for continuous data, regardless of the timing of these multiple ECG measurements.

3.7.2. Analysis Windows

Subject visits might not occur on protocol-specified days. Therefore, for the purposes of analysis, visit windows will be utilized when a single value at a visit is required for analysis.

Visit windows are defined for HCV RNA, vital signs and safety laboratory data. No analysis windows will be defined for health related quality of life data and pregnancy data.

All available HCV RNA data will be included in efficacy analysis, unless a subject starts alternative HCV medication. HCV RNA data collected after starting alternative HCV medication will be excluded. Imputation for missing HCV RNA values are described in Section 3.6. For safety data, subjects who are permanently discontinued from study drug will be included in safety analyses to last dosing date of any study drug + 30 days unless otherwise specified.

HCV RNA, vital signs, and safety laboratory test data collected up to the *last dose date of any study drug* + 2 days are considered to be on-treatment data and HCV RNA, vital signs and safety laboratory data collected after the *last dose date of any study drug* + 2 days are considered posttreatment data. On-treatment and posttreatment data will follow 2 different sets of visit windows.

Visit windows will be calculated from **Study Day 1** (ie, Study Day = collection date minus date **Study Day 1**; +1 if result is ≥ 0) for HCV RNA, vital signs and other safety laboratory data as shown in Table 3-1.

Table 3-1. On-Treatment Visit Windows for Selected Tests

Visit ID	On-Treatment Visit Windows for HCV RNA, Vital Signs and Safety Laboratory Data
Baseline	Study Day \leq 1
Week 1	$2 \leq$ Study Day \leq 11
Week 2	$12 \leq$ Study Day \leq 21
Week 4	$22 \leq$ Study Day \leq 35
Week 6	$36 \leq$ Study Day \leq 49
Week 8	$50 \leq$ Study Day \leq 63
Week 10	$64 \leq$ Study Day \leq 77
Week 12	$78 \leq$ Study Day \leq 98

HCV RNA, vital signs, and safety laboratory data collected after the *last dose date of study drug* + 2 days will be assigned to the posttreatment FU visit windows. Windows will be calculated from the *last dose date of study drug* (ie, FU Day = collection date minus the *last dose date of study drug*) as shown in Table 3-2.

Table 3-2. Post-treatment Visit Windows for Selected Tests

Off-Treatment FU Visit ID	Post-treatment Visit Windows for HCV RNA ^a (Days from Last Dose Date)	Vital Signs and Safety Laboratory Data ^b (Days from Last Dose Date)
FU-4	$21 \leq$ FU Day \leq 69	$3 \leq$ FU Day \leq 30
FU-12	$70 \leq$ FU Day \leq 146	N/A
FU-24	$147 \leq$ FU Day \leq 190	N/A

a SVR follow-up visit window (lower bound) must occur within 7, 14, and 21 days of target for SVR4, SVR12, and SVR24, respectively.

b Vital signs and safety labs will only be summarized for the 4-week follow-up visit (up to 30 days post last dose).

Qualitative assessments of whether the ECG is normal or abnormal will be assessed based on the following visit windows shown in Table 3-3:

Table 3-3. On-Treatment Visit Windows for ECGs

Visit ID	On-Treatment Visit Windows for ECG Data
Baseline	Study Day \leq 1
Week 1	$2 <$ Study Day \leq 18
End of Treatment	$18 <$ Study Day \leq Study Day of Last dose date +2

Note: ECGs are to be collected at screening, baseline, Week 1, Week 12 and End of Treatment. For purposes of analysis, Baseline will be the last available value prior to first dose and End of treatment is last available ECG on/prior to last dose date of study drug +2 day.

3.7.3. Selection of Data in the Event of Multiple Records in a Window

Depending on the statistical analysis method, single values may be required for each analysis window. For example, change from baseline by visit usually requires a single value, whereas a time-to-event analysis would not require 1 value per analysis window. When a single value is needed, the following rules will be used:

- Select the record closest to the nominal day (ie, visit weeks x 7 days) for that visit except for HCV RNA post-treatment follow-up visits, for which the latest record in the analysis window should be selected.
- If there are 2 visits equidistant from the nominal day within the analysis window, take the latest.
- If there is more than 1 record on the selected day, take the average (for continuous data) or the worst (for categorical data). If there are 2 values on the same day, the second may be a retest because there was a problem with the first test (eg, specimen hemolyzed). In cases where the first test is cancelled, the retest value should be used.
- For ECG end of treatment value, select the last value on/prior to last dose date of study drug +2. (if applicable)

4. SUBJECT DISPOSITION

4.1. Subject Enrollment

The number and percentage of subjects enrolled and treated by each investigator will be summarized by prior treatment experience (treatment naive and treatment experienced subjects) for China and Overall. The denominator for this calculation will be the number of subjects in the safety analysis set for that column.

4.2. Disposition of Subjects

A summary of subject disposition will be provided for China and Overall. This summary will present the number of subjects screened, rescreened, subjects not enrolled (with reasons), enrolled, enrolled and treated (ie, Safety Analysis Set), FAS, PK Analysis Set, and the number and percentage of subjects meeting the following criteria:

- Completed study treatment
- Discontinued study treatment (with summary of reasons for not completing the study treatment period)
- On study treatment (if applicable)
- Completed the study
- Did not complete the study (with summary of reasons for not completing the study)
- On study (ongoing; if applicable)

Among subjects who completed study treatment and who discontinued study treatment, the number and percentage of subjects will be summarized for:

- Who had no HCV posttreatment Week 4 assessment (No HCV FU-4 Assessment)
- Who had HCV posttreatment Week 4 assessment but no HCV posttreatment Week 12 assessment (With HCV FU-4 but No FU-12 Assessment)

If a subject did not have any HCV RNA assessment beyond 21 days after the last dose of any study drug (ie, lower bound of FU-4 visit for HCV), the subject is categorized as having “*No HCV FU-4 Assessment*”. If a subject had the HCV FU-4 assessment but did not have any HCV RNA assessment beyond 70 days after the last dose of any study drug (ie, lower bound of FU-12 visit for HCV), the subject is categorized as having “*With HCV FU-4 but No FU-12 Assessment*”.

The denominator for the percentages of subjects in each category will be the number of subjects in the safety analysis set for that column.

No inferential statistics will be generated.

A data listing of date of informed consent, first dose date, last dose date of study drug (study day), date completed study (study day), completed study treatment (yes/no), completed study (yes/no) and reasons for premature study treatment/study discontinuation will be provided. The last available observed nonmissing HCV RNA value prior to discontinuation and for up to 2 days after last dose of study drug will be included in this listing.

4.3. Extent of Exposure

4.3.1. Duration of Exposure to Study Drug

Duration of exposure to study treatment will be defined as (Last Dose Date of Study Drug – First dose Date of Study Drug + 1), regardless of temporary interruptions in study drug administration, and will be expressed in weeks (recorded to 1 decimal place, eg, 12.1 weeks).

Duration of exposure to the study drug will be summarized using descriptive statistics (sample size, mean, standard deviation [SD], median, first quartile [Q1], third quartile [Q3], minimum and maximum) and as the number of subjects exposed *through* (ie, cumulative counts): Baseline (Day 1); Week 1 (Day 7); Week 2 (Day 14); Week 4 (Day 28); Week 6 (Day 42); Week 8 (Day 56); Week 10 (Day 70); Week 12 (Day 84).

Summaries will be provided by prior treatment experience for China and Overall for the safety analysis set.

4.3.2. Adherence to Study Drug

Adherence will be calculated for LDV/SOF (tablets) as:

$(\text{Number of tablets taken}) \div (\text{Number of tablets prescribed at Baseline for study drug}) \times 100\%$

Note: If calculated adherence is greater than 100%, the result will be set to 100%.

4.3.2.1. Calculation of Number of Tablets Prescribed for Study Drug

For subjects who complete study drug or prematurely discontinue study drug for a reason other than virologic failure (ie, met virologic failure stopping criteria) the number of tablets prescribed is:

- Prescribed LDV/SOF (90 mg/400 mg) would require 84 tablets (ie, 1 tablet/day x 84 days) for the 12-week treatment period.

Subjects who prematurely discontinue study drug for lack of efficacy (ie, virologic failure) will have prescribed medications calculated for the number of study days at the first date when virologic stopping criteria were met (ie, substitute number of days to virologic failure [date of first of 2 consecutive measurements or a last available value meeting criteria] for 84 days).

4.3.2.2. Calculation of Number of Tablets Taken

The number of tablets taken for LDV/SOF during the treatment period will be calculated as the sum of (number of tablets dispensed – number of tablets returned) at each distinct dispensing period across all bottles/blister packs dispensed. For subjects who discontinue for virologic failure, bottles dispensed after the subject first met virologic failure criteria will not be included in calculations. If a bottle is dispensed, and the bottle is returned empty, then the number of tablets returned will be entered as zero. If a bottle is dispensed but not returned (missing), the number of tablets taken from that bottle will be counted as zero.

Descriptive statistics for adherence to LDV/SOF (sample size, mean, SD, median, Q1, Q3, minimum and maximum) along with the number and percentage of subjects belonging to adherence categories (e.g., < 80%, ≥ 80 to < 90%, ≥ 90%) will be provided by prior treatment experience for China and Overall for the safety analysis set.

No inferential statistics will be provided.

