5.5. Accountability for SOF/LDV FDC

The investigator is responsible for ensuring adequate accountability of all used and unused IMP. This includes acknowledgement of receipt of each shipment of IMP (quantity and condition). All used and unused IMP dispensed to subjects must be returned to the site.

SOF/LDV FDC accountability records will be provided to each study site to:

- Record the date received and quantity of IMP kits.
- Record the date, subject number, subject initials, the IMP kit number dispensed.
- Record the date, quantity of used and unused IMP returned, along with the initials of the person recording the information.

Subjects must be instructed to bring back all bottles of study medication in the original container at every post-baseline study visit through the end of treatment.

Study medication will be reconciled using medication pill counts at every post-baseline visit by the investigator or designee (e.g., pharmacist, study coordinator) in order to monitor the subject's adherence with the medication regimen.

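### For subjects stopped early for on-treatment virologic failure, the SAP's adherence numerator and denominator can end at different dates, so adherence can be overstated

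*SAP*

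**What the plan says.** Four SAP provisions and three protocol provisions bear on this.

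- **Ratio and cap.** SAP 4.3.2 divides tablets taken by tablets prescribed, and says "If calculated adherence is greater than 100%, the result will be set to 100" per cent.
- **Denominator.** SAP 4.3.2.1 gives completers, and subjects who stop for reasons other than virologic failure, a regimen that "would require 84 tablets (ie, 1 tablet/day x 84 days) for the 12-week treatment period". For subjects who stop early for virologic failure it says to "substitute number of days to virologic failure [date of first of 2 consecutive measurements or a last available value meeting criteria] for 84 days".
- **Numerator.** SAP 4.3.2.2 has tablets taken "calculated as the sum of (number of tablets dispensed – number of tablets returned) at each distinct dispensing period across all bottles/blister packs dispensed". For virologic-failure stops the only adjustment is: "For subjects who discontinue for virologic failure, bottles dispensed after the subject first met virologic failure criteria will not be included in calculations". A bottle that is never returned counts as zero tablets taken.
- **Use.** Adherence is tabulated by category (SAP 4.3.2.2). The split at 80% is also a listed SVR12 subset (SAP 3.4), shown with exact intervals and a forest plot (SAP 6.1.3).
- **Protocol.** Drug is dispensed at Day 1, Week 4 and Week 8 (Appendix 2). Confirmation of an on-treatment failure may take up to 2 weeks (3.5). On accountability, 5.5 says "Study medication will be reconciled using medication pill counts at every post-baseline visit".

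**The concern.** The denominator is cut by date and the numerator by bottle. A subject whose first failing sample falls between dispensing visits still holds an open bottle. If that subject keeps dosing while confirmation is awaited, the tablets from that bottle enter the numerator, but the days on which they were taken are not in the denominator. Late tablets then offset doses missed before failure, and the cap removes the one visible sign of the mismatch, a value above 100%.

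Dropping later bottles suggests that the SAP meant to align the two periods; the alignment is incomplete. Every subject under this rule is an on-treatment virologic failure, so the error falls on failures only. Moving one such subject from below 80% to 80% or above raises SVR12 in the low-adherence row and lowers it in the other, which weakens any visible link between missed doses and failure.

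**Working it through.** **Inputs.** F is the study day of the first failing sample (end of the denominator, SAP 4.3.2.1). S is the day dosing stops. Bottles are dispensed at about Days 1, 28 and 56 (protocol Appendix 2). The lag S − F is taken as 7 to 14 days: the upper end is the confirmation limit in protocol 3.5, and the lower end is an assumption because laboratory turnaround is not stated. Dosing is assumed to continue until confirmation. The date in the numerator rule is read as F.

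**The plan's own figure.** 1 tablet/day × 12 weeks × 7 days = 84 tablets, as stated.

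**Formula.** SAP adherence = min(100%, tablets taken from bottles dispensed up to F ÷ F). If no bottle is excluded and true adherence is a constant a, this is min(100%, a × S/F).

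**Example 1: F = 42, S = 56, 28 tablets before F and 14 after.** The Week 4 bottle was dispensed before F, so it counts to its return.
- SAP: (28 + 14)/42 = 100%
- Both terms to the failing sample: 28/42 = 66.7%
- Both terms to the stop: 42/56 = 75%

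Both consistent versions are below 80%; the SAP puts the subject in the ≥80% group.

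**Example 2: F = 70, S = 83 (before completion), 52 tablets before F and 13 after.**
- SAP: 65/70 = 92.9%
- To the sample: 52/70 = 74.3%
- To the stop: 65/83 = 78.3%

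**Constant true adherence.** The ≥80% group is reached when a ≥ 80% × F/S, and 100% is reported when a ≥ F/S.

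| F | S | a scored ≥80% | a scored 100% |
|---|---|---|---|
| 42 | 49 | 68.6% or more | 85.7% or more |
| 42 | 56 | 60% or more | 75% or more |
| 70 | 83 | 67.5% or more | 84.3% or more |

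**Where the effect shrinks, vanishes or reverses.**
- Low adherence still shows: F = 42, S = 56, a = 50% gives 50% × 56/42 = 66.7%, below 80%.
- Failure on a dispensing visit: F = 56, S = 70, a = 75%. If that day's bottle is treated as dispensed after failure, 42/56 = 75% and there is no inflation. If it is counted, (42 + 10.5)/56 = 93.8%. The SAP does not say which applies.
- A later bottle is dropped: F = 42, S = 63, a = 75% counts 0.75 × 56 = 42 tablets, not the 0.75 × 63 = 47.25 taken.
- Unreturned bottle: F = 42, full adherence, second bottle missing gives 28/42 = 66.7%, an understatement.

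**Subgroup illustration (assumed row size).** If the <80% row held 5 subjects with 1 failure, moving that failure out changes the row's SVR12 from 4/5 = 80% to 4/4 = 100%.

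**The case against.** The strongest reply is that the affected group may be empty. In the Japanese study (protocol 1.2.2.3), the three subjects among 341 without SVR12 were one relapse, one stop for rash and one death, so none was an on-treatment virologic failure. The two-sided 95% exact upper limit for 0/341 is 1 − 0.025^(1/341) = 1.1%, or about 2 of 200 Chinese subjects if that experience carries over. Subjects who relapse after completing treatment keep the 84-tablet denominator. By-subject listings of drug administration, accountability with adherence, and virologic failure are planned (SAP Appendix 1, Listings 6.1, 6.2 and 8.2), so a reviewer could check dosing in the few cases. All of this stands, and it limits the point to a small correction.

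A reader might infer three stronger things that the documents do not support.

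- *That the numerator always runs to the actual stop.* It does not: SAP 4.3.2.2 drops bottles dispensed after first failure, so the excess is limited to bottles already dispensed.
- *That poorly adherent failures are as a rule filed as fully adherent.* They can be, depending on timing. Example 1 needs a subject who missed a third of doses to miss none in the next 14 days, and it uses the full confirmation limit although protocol 3.5 asks for confirmation as soon as possible. With a 7-day lag it gives (28 + 7)/42 = 83.3%. At a constant 66.7% over 14 days it gives 66.7% × 56/42 = 88.9%. Both still cross 80%, but neither is 100%.
- *That a Week 10 failure who doses through Day 84 is also inflated.* That subject has completed the course and takes the 84-tablet denominator: (52 + 14)/84 = 78.6%, still below 80%.

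**Conclusion.** The point holds in a limited form. Followed exactly, the SAP gives a wrong adherence value for a subject who fails between dispensing visits and keeps dosing from an open bottle. Nothing else in either document corrects it. In Example 1 the overstatement is 33.3 percentage points against adherence to the sample and 25 against adherence to the stop. In Example 2 it is 18.6 and 14.6. Both examples cross the prespecified 80% boundary.

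This rests on dosing continuing during confirmation, on a lag near the 2-week limit for the largest values, and on bottles being returned. The misclassification is possible, not systematic. It reaches only the descriptive adherence table and the SVR12-by-adherence subgroup, with its forest plot. The primary binomial test is untouched. The point is minor, but worth correcting because the correction is nearly free.

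**What to change.** In SAP 4.3.2.1 and 4.3.2.2, use one cut-off date for both terms for subjects stopped early for virologic failure.

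- **Preferred:** end both terms at the last dose date defined in SAP 3.7.1, and include all bottles dispensed up to that date. In Example 1 this gives 42/56 = 75%. It also removes the question of whether a bottle dispensed on the day of the first failing sample counts.
- **Alternative:** keep the existing denominator and end the numerator at the pill count from the first failing visit. Protocol 5.5 requires these counts, but neither document shows that counts between dispensing visits reach the analysis database, so confirm that first.

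The cost is one or two sentences and a small programming change. The small downside of the preferred version is that it includes dosing days after the first failing sample, which cannot explain that sample.

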3.4. Examination of Subject Subsets

In addition to analyzing by groups according to prior treatment experience, the primary efficacy endpoint, SVR12, will be analyzed for the following subsets:

- age group on date of first dose of study drug (< 65 years, ≥ 65 years)
- sex (male, female)
- baseline BMI (< 25 kg/m², ≥ 25 kg/m²)
- cirrhosis (cirrhosis, absence of cirrhosis)
- response to prior HCV treatment (nonresponse, relapse/breakthrough, IFN intolerant) for treatment experienced subjects
- IFN eligibility (IFN eligible, IFN ineligible, IFN unwilling) for treatment naive subjects
- baseline HCV RNA (< 800,000 IU/mL, ≥ 800,000 IU/mL) and (< 5 log₁₀ IU/mL, ≥ 5 log₁₀ IU/mL)
- baseline ALT (≤ 1.5 × ULN, > 1.5 × ULN)
- IL28B (CC, Non-CC (CT, TT))
- adherence to study drug (<80%, ≥ 80%)

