6.1.3. Subgroup Analysis of the Primary Efficacy Endpoint

Point estimates and 95% exact confidence intervals of the SVR12 rates by prior treatment experience for China and Overall (i.e., China plus Korea plus Taiwan) will be displayed for each subgroup outlined in Section 3.4. The 2-sided 95% exact confidence intervals will be based on Clopper-Pearson method {Clopper 1934}.

A Forest plot will graphically present estimates and 95% confidence intervals of SVR12 rates for each of the subgroups.

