Appendix 1. Table of Contents for Statistical Tables, Figures, and Listings

Table Number	Title	Analysis Set
1	Subjects Enrolled and Treated by Investigator	Safety Analysis Set
2	Subject Disposition	Screened Subjects
3	Reasons for Screen Failure	Screened Subjects
4	Demographics and Baseline Characteristics	Safety Analysis Set
4.1	Summary of Categories for Interferon Eligibility and Reasons for Interferon Ineligible	Safety Analysis Set
4.2	Summary of Categories for Response to Prior HCV Treatment and Reasons for Interferon Intolerance	Safety Analysis Set
5	Duration of Exposure to Study Drug	Safety Analysis Set
6	Concomitant Medications	Safety Analysis Set
7	Adherence to Study Drug	Safety Analysis Set
8.1	SVR12	Full Analysis Set
8.2	SVR12 by Subgroup	Full Analysis Set
9	Concordance between SVR12 and SVR24	Full Analysis Set
10	Virologic Outcome	Full Analysis Set
11	Proportion of Subjects with HCV RNA Less than LLOQ While on Treatment by Visit	Full Analysis Set
12	SVR by Visit During Posttreatment Follow-Up	Full Analysis Set
13	HCV RNA (log ₁₀ IU/mL) and Change from Baseline by Visit Through Week 12	Subjects in China in Full Analysis Set
14	Proportion of Subjects with ALT Normalization by Visit	Full Analysis Set with ALT>ULN at Baseline
15	Adverse Events: Brief Summary	Safety Analysis Set
16	All Treatment-Emergent Adverse Events	Safety Analysis Set
17	Treatment-Emergent Treatment-Related Adverse Events	Safety Analysis Set
17.1	Treatment-Emergent Treatment-Related Adverse Events by Preferred Term	Safety Analysis Set
18	Grade 3 or 4 Treatment-Emergent Adverse Events	Safety Analysis Set
19	Grade 3 or 4 Treatment-Emergent Treatment-Related Adverse Events	Safety Analysis Set
20	Grade 2, 3, or 4 Treatment-Emergent Adverse Events	Safety Analysis Set
21	Grade 2, 3, or 4 Treatment-Emergent Treatment-Related Adverse Events	Safety Analysis Set

Table Number	Title	Analysis Set
22	Adverse Events Leading to Permanent Discontinuation from LDV/SOF	Safety Analysis Set
23	Treatment-Emergent Serious Adverse Events	Safety Analysis Set
24	Treatment-Emergent Treatment-Related Serious Adverse Events	Safety Analysis Set
25	All Deaths	Safety Analysis Set
27	Treatment-Emergent Adverse Events Occurring in At Least 5% of Subjects by Preferred Term	Safety Analysis Set
28	Adverse Events Leading to Permanent Discontinuation of LDV/SOF by Preferred Term	Safety Analysis Set
29	Treatment-Emergent Serious Adverse Events by Preferred Term	Safety Analysis Set

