4.2	Median (Q1, Q3) Change from Baseline in HCV RNA (\log_{10} IU/mL) by Visit Through Week 12	Subjects in China in Full Analysis Set
4.3	Mean \pm SD in HCV RNA (\log_{10} IU/mL) by Visit Through Week 12	Subjects in China in Full Analysis Set
4.4	Median (Q1, Q3) in HCV RNA (\log_{10} IU/mL) by Visit Through Week 12	Subjects in China in Full Analysis Set
5.1	Median (Q1, Q3) ALT (U/L) by Visit	Safety Analysis Set
5.2	Median (Q1, Q3) AST (U/L) by Visit	Safety Analysis Set
5.3	Median (Q1, Q3) Total Bilirubin (mg/dL) by Visit	Safety Analysis Set
5.4	Median (Q1, Q3) Alkaline Phosphatase (U/L) by Visit	Safety Analysis Set
5.5	Median (Q1, Q3) Hemoglobin (g/dL) by Visit	Safety Analysis Set
5.6	Median (Q1, Q3) Reticulocytes ($\times 10^3 / \mu\text{L}$) by Visit	Safety Analysis Set
5.7	Median (Q1, Q3) WBC ($\times 10^3 / \mu\text{L}$) by Visit	Safety Analysis Set
5.8	Median (Q1, Q3) Neutrophils ($\times 10^3 / \mu\text{L}$) by Visit	Safety Analysis Set
5.9	Median (Q1, Q3) Lymphocytes ($\times 10^3 / \mu\text{L}$) by Visit	Safety Analysis Set
5.10	Median (Q1, Q3) Platelets ($\times 10^3 / \mu\text{L}$) by Visit	Safety Analysis Set
6	Mean \pm SD Change from Baseline in SF-36 Quality of Life Questionnaire by visit	Full Analysis Set

Listing Number	Title	Analysis Set
1	Inclusion and Exclusion Criteria	Subjects Not Treated
2.1	Subjects Who were Excluded from Safety and Full Analysis Sets	All Enrolled Subjects
2.2	Subjects Enrolled and Treated Who Did Not Meet Eligibility Criteria	Safety Analysis Set
3	Subject Disposition	Safety Analysis Set
4.1	Subject Demographics and Baseline Characteristics	Safety Analysis Set
4.2	Cirrhosis Determination	Safety Analysis Set
4.3	Interferon Ineligible Reasons	Safety Analysis Set
4.4	Interferon Intolerant Reasons	Safety Analysis Set
4.5	Response to Prior HCV Treatment	Safety Analysis Set
5	Medical History	Safety Analysis Set
6.1	Study Drug Administration	Safety Analysis Set
6.2	Study Drug Accountability and Adherence	Safety Analysis Set
7	Prior and Concomitant Medications	Safety Analysis Set
8.1	HCV RNA (log ₁₀ IU/mL) and Change from Baseline	Safety Analysis Set
8.2	Subjects with Virologic Failure	Safety Analysis Set
8.3	Subjects with Postbaseline Hemoglobin < 10 g/dL or < 8.5 g/dL	Safety Analysis Set
9	SF-36 Quality of Life Questionnaire	Safety Analysis Set
10	All Adverse Events	Safety Analysis Set
11	Grade 3 or 4 Adverse Events	Safety Analysis Set
12	Adverse Events Leading to Permanent Discontinuation from LDV/SOF	Safety Analysis Set

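### Counting an unreturned bottle as zero tablets over a denominator of 84 puts a fully dosed subject in the below-80% adherence rows (descriptive outputs only)

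*SAP*

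**What the plan says.** SAP 4.3.2 defines adherence as tablets taken divided by tablets prescribed, and truncates high values: "If calculated adherence is greater than 100%, the result will be set to 100" percent.

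**Denominator (SAP 4.3.2.1).** For completers and for those who stop for a reason other than virologic failure: "Prescribed LDV/SOF (90 mg/400 mg) would require 84 tablets (ie, 1 tablet/day x 84 days) for the 12-week treatment period". For those who stop for lack of efficacy, the days to virologic failure replace 84.

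**Numerator (SAP 4.3.2.2).** Dispensed minus returned, summed over bottles. A bottle returned empty counts as fully taken. For a bottle that does not come back: "If a bottle is dispensed but not returned (missing), the number of tablets taken from that bottle will be counted as zero". For virologic-failure discontinuations, bottles dispensed after the failure criteria were first met are left out.

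**Where the result goes.** SAP 4.3.2.2 summarises adherence as a continuous variable and in categories (Table 7). SAP 3.4 makes adherence, cut at 80%, an SVR12 subgroup. That subgroup appears in Table 8.2 ("SVR12 by Subgroup") and in the figure described in SAP 6.1.3: "A Forest plot will graphically present estimates and 95% confidence intervals of SVR12 rates for each of the subgroups". No test is attached to any of these outputs.

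**The concern.** Two subjects with identical dosing can differ by a whole bottle because one of them did not bring back an empty container. The rule treats the lack of a return count as evidence that nothing was taken, and the denominator is not reduced to match. At the extreme, a subject who returned no bottle would score 0%, although Protocol 6.4.1 requires the first dose to be observed.

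For mean adherence this is a cautious convention. For the SVR12 subgroup it is not. Protocol 1.2.2.2 and 1.3 report SVR12 above 93% overall in earlier studies of this regimen, so misplaced full takers are likely to be responders. Putting them in the below-80% row can raise the response rate shown for poor adherence and make missed doses look less important than they are. If that row is small, a few unreturned bottles could dominate it.

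**Working it through.** **Inputs**
- Tablets prescribed: 84 (SAP 4.3.2.1). Reproduced: 1 tablet/day × 12 weeks × 7 days = 84.
- Tablets per bottle: 28 in China, 30 in Korea and Taiwan (Protocol 5.2.2).
- Dispensing visits: Day 1, Week 4 and Week 8 (Protocol Appendix 2; SAP Appendix 2).
- Bottles per visit: not stated. One per visit, with no replacement, is an assumption; 3 × 28 = 84 fits it.

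**The 80% cut.** 0.80 × 84 = 67.2. Since 67/84 = 79.8% and 68/84 = 81.0%, at least 68 tablets must be counted, and at most 84 − 68 = 16 can go uncounted.

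**Highest possible score with one bottle unreturned and a denominator of 84**
- 28-tablet bottles: (28 + 28)/84 = 56/84 = 66.7%.
- 30-tablet bottles: (30 + 30)/84 = 60/84 = 71.4%.

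Both are below 80%.

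**Virologic-failure discontinuation.** Suppose a China subject empties bottles 1 and 2, receives bottle 3 at Week 8, first meets failure criteria on Day 70, and never returns bottle 3. The score is 56/70 = 80.0%, which is in the upper row. The cap above therefore does not apply to this group.

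**Zero rule against counting the unreturned bottle as fully taken (denominator 84)**

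| Case | Zero rule | Fully taken | Same category? |
|---|---|---|---|
| China, all 84 taken, any one bottle unreturned | 56/84 = 66.7% | 84/84 = 100% | No |
| Korea/Taiwan, all 84 taken as 30 + 30 + 24, bottle 1 or 2 unreturned | 54/84 = 64.3% | 84/84 = 100% | No |
| The same, bottle 3 unreturned | 60/84 = 71.4% | 90/84, capped at 100% | No |
| China dropout, bottle 1 returned empty, bottle 2 unreturned | 28/84 = 33.3% | 56/84 = 66.7% | Yes, below 80% |
| China, bottles 1 and 2 returned empty, stops after Week 8, bottle 3 unreturned | 56/84 = 66.7% | 84/84 = 100% | No |

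**Effect per subject.** In a China group of about 100, each fully dosed subject with one unreturned bottle moves 1 percentage point from the top category to the below-80% category. Mean adherence falls by (100 − 66.7)/100 = 0.33 points.

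**Effect on the SVR12 row (assumed counts, for illustration only).** One responder among two true non-adherers is 1/2 = 50%. Adding four misplaced responders gives 5/6 = 83%.

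**The case against.** The rule is explicit and prespecified: no credit is given for tablets that cannot be verified. Non-return is itself a departure from Protocol 5.5, which requires all bottles to be brought back at every post-baseline visit and pill counts to be made, so it may be rare. Exposure duration (SAP 4.3.1) does not depend on bottle returns, and Listing 6.2 ("Study Drug Accountability and Adherence") may let a reader see the underlying data. All of this stands. It limits the point to one of presentation, but it does not correct the rows in Table 7, Table 8.2 or the forest plot.

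Three stronger readings are tempting, and the documents do not support them.
- *Every subject with an unreturned bottle falls below 80%.* This is not so. The denominator for virologic-failure discontinuations is days to failure, and 80% can then be reached.
- *The rule contradicts SAP 3.6.1*, which says "Except for the imputation rules described above, values for other missing data (including all safety data) will not be imputed". A specific adherence rule reasonably governs over a general sentence on missing data. That SAP 4.3.2.2 gives no reason for the rule is not a contradiction.
- *Table 7 has no room for an unknown category.* SAP 4.3.2.2 offers its categories only as examples. Only the two-level subgroup in SAP 3.4 is fixed.

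**Conclusion.** The point holds as a minor one. For subjects with a denominator of 84, and assuming one bottle per dispensing visit without replacement, a single unreturned bottle limits adherence to 66.7% (China) or 71.4% (30-tablet bottles). This forces the subject into the below-80% rows whatever was taken. Korea and Taiwan enter only through the Overall outputs of this SAP.

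A reader might infer that the trial's efficacy conclusion is at risk. It is not: the primary test in SAP 6.1.2 uses the Full Analysis Set and makes no use of adherence, and the analysis sets and exposure duration are also unaffected. Nor can one say what share of the below-80% group is misplaced, because no non-return rate is given.

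**What to change.** Keep the rule in SAP 4.3.2.2 as the main convention, and add two things for China and Overall alike.

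1. Report the number of subjects with an unreturned bottle in Table 7 and beside the adherence rows of Table 8.2.
2. Add one sensitivity classification from the existing dispensing and return records. Count the unreturned bottle as fully taken, with the 100% cap already in SAP 4.3.2. Where the category differs between the two counts, show the subject as 'unknown (bottle not returned)'.

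The cost is a few lines of SAP text and a little extra programming. The downside is that, in the sensitivity display only, some true non-adherers become unknown. The subject who stops after Week 8 and keeps bottle 3 is one example. Clear early dropouts, such as the 33.3% to 66.7% case, stay below 80% under both counts.
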